We designed the present randomized trial to test whether 12 weeks of supervised weekly Kundalini yoga class and a brief daily home meditation practice can improve cognitive function among older women with high AD risk compared to weekly classes of memory training with daily homework. Our choice of interventions is based on prior studies of mind-body exercise in older adults that revealed robust cognitive benefit, as well as our own studies of this intervention compared to cognitive memory training in older adults with MCI. Kundalini yoga has also been observed to impact the frontal lobes, likely due to increased cerebral blood flow ([name] et al., 2013b).

The primary outcome will be memory performance at 12 weeks (i.e., immediately post-treatment).

Secondary outcomes include measures of executive functioning and changes in brain structure and connectivity.

Specific Aim 1: To evaluate effects of Kundalini Yoga+ Kirtan Kriya (KK+KY) and Memory Enhancement Training (MET) on memory performance in women with high AD risk.

Hypothesis 1: Improved memory performance will be observed in women receiving KK+KY and MET at 12 weeks compared to baseline.

Specific Aim 2: To test the efficacy of KK+KY vs. MET for improving executive functioning including working memory.

Hypothesis 2: KK+KY will improve performance in executive functioning to a greater extent than MET.

Exploratory Aim 3a: To test the effects of MET vs. KK+KY on structural and functional connectivity and task-related activation for working and episodic memory.

Hypothesis 3a: Compared to MET, KK+KY will be associated with greater improvement in connectivity in regions associated with working and episodic memory.

Exploratory Aim 3b: To test the effects of MET vs. KK+KY on levels of cellular and genomic markers of inflammation, telomerase activity level, and telomere length after 12 weeks and at 6 and 12 month follow-up.

Hypothesis 3b: Compared to MET, KK+KY will be associated with decreases in cellular and genomic markers of inflammation and increases in telomerase activity level and telomere length after 12 weeks and at 6 and 12 month follow-up.

Exploratory Aim 3c: To explore whether KK+KY results in reduced cardiovascular risk factors compared to MET, and whether this effect will correlate temporally with changes in fMRI measures and clinical outcomes.

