Measures and Outcomes: All instruments provide a comprehensive assessment of cognition, mood, quality of life, well-being, mindfulness and resilience. Diagnosis will be determined on study entry. *All outcome measures will be administered at baseline, week 12, and 6 and 12 months, or upon early termination. Primary and secondary outcome and safety measures will be administered at each assessment visit.*

The Hopkins Verbal Learning Test-Revised (HVLT-R)(Benedict, Schretlen, Groninger, & Brandt, 1998) delayed recall will be administered at baseline to identify memory impairment.

The Beck Depression Inventory will be used to rule out current clinically-significant depressive symptoms.

Inter-rater reliability for all instruments will be established at the beginning of the trial. Drs. [name] and [name] will administer clinician-administered instruments and will be trained to reliability (current inter-rater correlation coefficient (ICC) \geq 0.9.).

Assessment: Memory performance as determined by neuropsychological evaluation (described below) is the primary outcome of interest. Behavioral outcome assessments will be performed by raters blind to treatment assignment.

Domain	Test	Administration Time
	HVLT (delayed recall)	30 min
Memory	WMS-IV (Logical Memory II delayed recall)	30 min
	Rey-Osterreith Complex Figure 3-min Delay	5 min
Executive Function/	Stroop Interference	5 min (computerized)
working memory	Trails B	5 min
	Trails A	3 min
Attention/ processing speed	Digit Span	5 min
	Stroop color and word	(no time added)
	CFL/FAS/PRW fluency	3 min
Language Fluency	Animal Fluency	1 min
	Boston Naming Test	15 min
Premorbid Cognitive Function	Wechsler TOPF	5 min

 Table 3. Neuropsychological test battery

Neuropsychological tests will be administered at baseline and at the 6- and 12-month follow-up. We will use a focused test battery developed by [name] that is highly sensitive to memory deficits. Because memory function is the main target of MET interventions, this will be the primary outcome. Specifically, **the primary**

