outcome will be an average of the participant's z-scores on three tests. Two of these tests will be of verbal memory tests: 1) the Hopkins Verbal Learning Test (HVLT) (total and delayed recall scores) (Shapiro et al., 1999), and (2) the Wechsler Memory Scale (WMS-IV) (immediate and delayed) and one will be of visual memory (the Rey-Osterreith Complex Figure 3-minute delay recall). The secondary outcome measure of executive functioning will include Trail Making B and Stroop Color-Word Interference tests to estimate mental flexibility and inhibition/adjustment of behavior. Tests of language fluency will include Animal fluency and CFL Letter Fluency to assess strategic searching/organization of verbal knowledge, as well as the Boston Naming Test. The battery will also include measures of attention/ processing speed which are commonly impaired in the geriatric population according to prior research by our group (Schneider, [name], Siddarth, & [name], 2012) and others (Alexopoulos, Kiosses, Klimstra, Kalavam, & Bruce, 2002; Bhalla et al., 2009; Butters, 2004; Favrod et al., 2015; Lockwood, Alexopoulos, & van Gorp, 2002). These tests place significant demand on mental operations that require speed, manipulation and monitoring of information that is in conscious awareness (Trail Making A; Digit Span; Stroop Color and Word). Most of the measures have 2 or 4 alternate forms so that unique forms may be administered to participants during repeat testing. We include both traditional, standardized tests and computerized tests for enhanced sensitivity of the battery to potential intervention effects and so that our results can also be compared with other findings in the literature. In addition to the cognitive outcome measures, we will include the TOPF to estimate pre-morbid cognitive functioning.

Secondary clinical outcome measures will include the Clinical Global Impression- Severity and Improvement scale (CGI)(Busner, Targum, & Miller, 2009) to quantify overall severity and clinical improvement over time (2 min). Subjective memory complaints will be assessed via the 10-item Memory Functioning Questionnaire scale. The Beck Depression Inventory (BDI) (Beck, Steer, & Brown, 1996; Beck, Steer, & Carbin, 1988), a self-assessment scale of depression (5 min), will also be administered, as will the Hamilton Anxiety scale.

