Pain will be assessed via the Brief Pain Inventory (BPI) Short Form, a validated scale for rapidly assessing the severity of pain and its impact on functioning (Cleeland, 1989).

Safety Evaluations: All participants will be interviewed about their recent history of psychiatric and medical illnesses, psychosocial stressors, and current medications. We will use the UKU Side Effect Rating Scale (Lingjærde, Ahlfors, Bech, Dencker, & Elgen, 1987), a rating scale for monitoring adverse events which will be completed at each assessment visit.

Domains of Assessment	Screen	Baseline	Week 6 (after class)	Week 12	Week 24	Week 48
Cognitive						
Clinical Dementia Rating	Х					
MMSE	Х			Х	Х	Х
Neuropsychological battery		Х			Х	Х
Memory Functioning	Х			Х	Х	Х
Psychosocial						
Beck Depression Inventory	Х			Х	Х	Х
Hamilton Anxiety	Х			Х	Х	Х
Perceived Stress Scale	Х			Х	Х	Х

Table 4. Assessment schedule.

Resilience (CD-RISC Scale)	х			x	x	x
Emotion Regulation	Х		Х	Х	Х	Х
SF-36 (QOL)	Х			Х	Х	Х
Duke Social Support	Х			Х	Х	Х
Monetary Choice	Х			Х	Х	Х
Medical						
CIRS-G	Х			Х		
Stroke Risk	Х			Х		
Clinical ECG	Х					
Brief Pain Inventory	Х			Х	Х	
Other						
Demographics / medical and reproductive history and medications	х					
Monitoring for new treatments		х	Х	X	Х	x
Treatment credibility		X (wk 2)		Х		
Clinical Global Improvement				X	х	x
Family history of dementia	Х					
Physical Activity and Meditation Practice	Х			Х	х	X
Adverse reactions		Х	Х	Х	Х	Х
Cellular Biomarkers						
Telomerase levels		Х		Х	Х	
Telomere length		Х		Х	Х	
Cardiac Biomarkers						
Lipid panel, hsCRP, HbA1c, TSH, electrolytes, CBC		x		х	х	
BP, HR, weight		Х		Х	Х	Х
Molecular Biomarkers						
Cytokine gene polymorphisms		x		x	х	
Microarrays (GWAS expression)		X		Х	х	
Imaging Biomarkers						
Structural MRI		Х		Х		
fMRI		Х		Х		
ANS Biomarkers						

Breathing rate	X	X	X	
End-tidal CO ₂	X	Х	Х	
ECG	X	Х	Х	
Continuous blood pressure	X	Х	Х	
Skin face temperature	X	X	Х	
Electromyogram	Х	Х	Х	
Spirometry	X	X	Х	
Galvanic skin response	X	Х	Х	
ANS challenges	X	X	Х	

Inflammatory biomarkers: Inflammatory signaling will be measured by assay of activation of NF-κB using intranuclear staining and flow cytometric analyses, given its associations with mood (Koo, Russo, Ferguson, Nestler, & Duman, 2010; Pace & Miller, 2009).

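### Table 4 schedules no CGI-Severity rating before treatment, although the text makes severity over time a secondary clinical outcome and asks for every outcome measure at baseline

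*Combined protocol and SAP*

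**What the plan says.** **CGI.** The paragraph on secondary clinical outcome measures names the "Clinical Global Impression- Severity and Improvement" scale, with the stated purpose "to quantify overall severity and clinical improvement over time" and an administration time of 2 minutes. The Measures and Outcomes section sets a general rule: "All outcome measures will be administered at baseline, week 12, and 6 and 12 months, or upon early termination". It adds that secondary outcomes are collected at each assessment visit. Table 4 carries one CGI row, "Clinical Global Improvement", marked at weeks 12, 24 and 48.

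**NF-κB.** The Inflammatory biomarkers text states: "Inflammatory signaling will be measured by assay of activation of NF-κB using intranuclear staining and flow cytometric analyses". That sentence gives no visit, and Table 4 has no row for the assay. The same run of text ends by planning blood draws at baseline, 12 weeks and 6 months. Hypothesis 3b predicts that "KK+KY will be associated with decreases in cellular and genomic markers of inflammation", at 12 weeks and at the 6- and 12-month follow-ups.

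**Genotype.** Table 4 marks "Cytokine gene polymorphisms" at baseline, week 12 and week 24.

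**The concern.** Severity over time needs a starting value. A schedule table is what staff usually work from, and this one gives no instruction to rate CGI-Severity at any visit before treatment. A clinician's global severity rating cannot be reconstructed once the intervention has begun, so an omission in the table becomes permanently missing data. At stake is whether one secondary clinical outcome can be analysed as change, or adjusted for its baseline value. The primary memory outcome is not involved.

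The NF-κB and genotype rows raise a lesser worry: the table and the text do not describe the same set of assays, so the laboratory has to infer what to run and when.

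**Working it through.** No formula underlies the main point. The check sets the text beside the marks in Table 4.

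| Measure | Text | Table 4 |
|---|---|---|
| CGI-Severity | Secondary clinical outcome; general rule includes baseline | No row |
| CGI-Improvement | Secondary clinical outcome | Weeks 12, 24, 48 |
| Memory Functioning, BDI, Hamilton Anxiety (same paragraph as CGI) | Secondary clinical outcomes | Screen, weeks 12, 24, 48 |
| NF-κB activation | Assay described; no visit given | No row |
| Microarrays | Baseline, week 12, 6 months | Baseline, weeks 12, 24 |
| hsCRP | Not scheduled in the biomarker text | Baseline, weeks 12, 24 |
| Cytokine gene polymorphisms | No assay or analysis described | Baseline, weeks 12, 24 |

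**1. Is CGI the exception among its neighbours?** Yes. The other three measures in that paragraph all have a screening mark. CGI alone has no mark before treatment.

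**2. Does the general rule settle the conflict?** Not reliably, because the documents depart from it elsewhere. The text later places neuropsychological tests at baseline and the 6- and 12-month follow-ups, and Table 4 likewise has no week 12 mark for that battery. The Brief Pain Inventory has no week 48 mark. Imaging is at baseline and week 12 only. Staff therefore cannot assume that the rule overrides the table. Nor can the rule be applied literally to the one CGI row present, since improvement cannot be rated at baseline.

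**3. What is lost if Table 4 is followed?**
- If the row means Improvement only, Severity is never rated.
- If the row is shorthand for both parts, Severity is rated at three post-treatment visits. The arms can still be compared on those levels, because they were randomised.
- On either reading, change from baseline is undefined and baseline adjustment is impossible. This would apply to all 100 planned women.
- Improvement is a rating of change, so its blank baseline cell is correct.

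**4. NF-κB.** Table 4's Cellular Biomarkers block lists only telomerase and telomere length. The three planned draws make samples before and after treatment possible, and the Exploratory Hypotheses paragraph plans mixed models for the inflammatory measures. Assigning the assay to those draws is an inference, because its own sentence names no visit. No blood draw is planned at 12 months, so the 12-month part of Hypothesis 3b has no blood sample behind it.

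**5. Polymorphisms.** An inherited genotype does not change, so 2 of the 3 marks carry no information. The ceiling is 2 × 100 = 200 repeat assays. Using the 10% losses in the Recruitment section, about 90 women remain at 12 weeks and 90 × 0.9 = 81 at 6 months, giving 90 + 81 = 171. The only use of genotype mentioned, linking it with autonomic and respiratory function, needs one measurement. The row may instead be mislabelled.

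**The case against.** The strongest reply is that the text already supplies the baseline. The general rule covers all outcome measures, CGI-Severity is one of them, and the row in Table 4 is a change rating that should have no baseline mark. On that view the defect is clerical, in a study run by one institution's team, for a measure that the Data analysis section never names. Much of this stands. It shows that a missing baseline is a risk that depends on which passage staff follow, not a documented fact. It does not remove the conflict, for the reasons in step 2 of the working.

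A reader might go further and infer that Table 4 leaves CGI and the inflammation markers of Hypothesis 3b unable to show change. The documents do not support that. The text asks for outcomes at baseline, blood is planned at three visits, longitudinal models are specified for the inflammatory measures, and microarrays and hsCRP each have three scheduled visits. Hypothesis 3b names no particular cellular marker, so treating NF-κB activation as that marker is itself an inference. Table 4 also does not list every procedure (diffusion imaging and arterial spin labelling have no rows of their own), so a missing row is weak evidence that an assay will not be done.

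A reader might also infer that raters of Improvement would have no starting point. Table 4 records several clinical scales at screening and the neuropsychological battery at baseline, so they would have information to work from.

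**Conclusion.** The concern holds as a conflict between table and text that puts the pre-treatment CGI-Severity rating at risk. If Table 4 governs, that rating is missing for every woman and CGI-Severity cannot be analysed as change or adjusted for baseline. If the general rule governs, the rating exists and only the table is wrong. The documents do not say which applies. Because the loss would be irreversible and the remedy is small, the conflict should be resolved. It affects one secondary clinical measure, not the primary outcome.

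The NF-κB and polymorphism rows are minor reconciliation. The first is missing detail; the second is redundant or mislabelled and changes no result.

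The conclusion assumes that the columns of Table 4 are read correctly. The marks were read from extracted text, where they line up consistently with neighbouring rows. They should be confirmed on the laid-out page.

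**What to change.** **Main change.** Add a CGI-Severity row to Table 4 at baseline, before randomisation, and at weeks 12, 24 and 48. Keep CGI-Improvement at weeks 12, 24 and 48. The COVID-19 Questionnaire and Assessment paragraph refers to active participants, so enrolment had begun by this version. The sponsor should therefore also report which enrolled women already have a baseline Severity rating.

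**Minor reconciliation in the same amendment.**
- List the NF-κB activation assay at the existing draws (baseline, week 12, 6 months), and state that Hypothesis 3b's 12-month claim has no planned blood draw.
- Reduce the cytokine gene polymorphism row to one measurement, treated as a fixed characteristic, or correct its label if another assay was meant.

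**Cost.** One table amendment. At the protocol's 2 minutes for the CGI, the added baseline rating takes at most 2 × 100 = 200 minutes across the planned sample. If Table 4's CGI row covers Improvement only, rating Severity at the three later visits still falls within the CGI time the text already plans. The NF-κB assay is already promised and needs no new draw. Genotyping once saves work.

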Microarray-based genome-wide transcriptional analyses will be used identify the molecular inflammation-related signaling pathways that are plausible candidates for molecular mediators of inflammation (e.g., NF-B) (Cole, 2010; Irwin, Olmstead, & Motivala, 2008; Irwin, Wang, Campomayor, Collado-Hidalgo, & Cole, 2006) and

glucocorticoid receptor-related signaling pathways that may underlie increased inflammatory signaling (Cole et al., 2007; G. E. Miller et al., 2008) with measures performed at baseline, week 12, and at 6months, as described previously (Cole et al., 2007; G. E. Miller et al., 2008). Expression data will be subject to quantile normalization, with differentially expressed genes identified based on False Discovery Rate analyses controlling false positive errors at 5%, and subsequent TELiS bioinformatics analysis of GR target motifs within the promoters of genes up-regulated in KK+KY vs. MET. Confirmatory RT-PCR analyses will be conducted on a subset of 12 differentially expressed transcripts to confirm microarray indications (Cole et al., 2007; G. E. Miller et al., 2008). We will assess the activity of telomerase level and TL at baseline, weeks 12 and 6month follow-up to monitor changes. The protocol will be the same as the one used previously by Jacobs and colleagues (Jacobs et al., 2011). Quantification of telomerase activity will be measured from the extract using the telomeric repeat amplification protocol (TRAP) as previously described (Kim & Wu, 1997) with a commercial kit (TRAPeze®, Chemicon, Temecula, CA). We will assess other factors related to inflammation during our baseline assessment and throughout the trial (e.g., alcohol, smoking, BMI, physical activity; use of NSAIDs, and recent infections when samples are

		•	
Sequence #	Sequence type	Acquisition time	Protocol type
	1. Localizer		-21: -
1.1	Localizer	0:00:09	HCP
1.2	AAHScout	0:00:14	HCP
1.3	Localizer_aligned	0:00:21	HCP
	2. T1-weighted image)	
2.1	T1w setter	0:00:02	HCP
2.2	T1w MPR vNav 4e	0:08:22	HCP
	3. T2-weighted image)	
3.1	T2w setter	0:00:03	HCP
3.2	T2w_SPC_vNav	0:06:35	HCP
	4. Resting state fMR		
4.1	SpinEchoFieldMap_AP	0:00:09	HCP
4.1	SpinEchoFieldMap_PA	0:00:09	HCP
4.3	Cal_800TR	0:00:30	HCP
4.4	rfMRI_REST_AP	0:06:41	HCP
4.5	rfMRI_REST_PA	0:06:41	HCP
	5. tfMRI N-back task		
5.1	task fMRI N-back	010:00	HCP
5.2	SpinEchoFieldMap_AP	0:00:09	HCP
5.3	SpinEchoFieldMap_PA	0:00:09	HCP
	6. task fMRI face nami	ng	
6.1	task fMRI face naming	0:05:25	HCP

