6.2	SpinEchoFieldMap_AP	0:00:09	HCP
6.3	SpinEchoFieldMap_PA	0:00:09	HCP
	7. Diffusion-weighted im	lage	
7.1	dMRI dir98 AP	0:05:38	HCP
7.2	dMRI_dir98_PA	0:05:38	HCP
	8. Arterial spin labelin	g	
8.1	PCASLhr_SpinEchoFieldMap_AP	0:00:09	HCP
8.2	PCASLhr_SpinEchoFieldMap_PA	0:00:09	HCP
8.3	mbPCASL_PA	0:05:29	HCP
	9. Magnetic resonance spectrosco	opy (optional)	
9.1	svs_edit_859G_WS	0:08:40	Siemens
9.2	svs_edit_859G_NWS	0:00:14	Siemens
1	0. High-resolution hippocampus str	ucture (optional)
10.1	TSE HiResHp	0:03:31	HCP
Total time (excluding shimming and set-up)	1:05:25	

collected). This will require 8 tablespoons of blood to be drawn at 3 time points (baseline, 12 weeks, and 6-month follow up).

Imaging Biomarkers: Imaging data will be acquired from each subject **at baseline and at 12- weeks postrandomization** on a Siemens 3T Prisma system using a 32-channel head coil. Each scanning session will last 60 minutes and include 1) high-resolution T1- and T2 weighted structural scans (0.8 mm³ voxel size) using protocols developed for the Human Connectome Project (HCP) Lifespan Project (www.humanconnectome.org), which will be used for registration and to measure morphometric features as may be included as covariates and used for the detection and quantification of WMHs and CSF; and 2) three separate multiband EPI sequences with enhanced spatial (2 mm³) and temporal (TR: 720 ms) resolution and anterior-posterior/posterior-anterior (AP/PA) phase encoding to correct for anatomic distortions for the acquisition of rs- and task-related fMRI data used for the examination of working memory processing and functional connectivity. In addition, localizers and

field maps to correct for EPI anatomic distortions will be acquired. The morphometry sequences are optimized for determining brain tissue contrast with reduced distortion (van der Kouwe, Benner, Salat, & Fischl, 2008).

Functional Imaging: Analysis of rs-fMRI data will determine whether KK+KY leads to plasticity in brain network activity. To address our hypothesis that KK+KY versus MET will result in improved executive functioning (working memory) we will employ the N-back task. During resting periods and tasks, we will also assess physiological measures, including respiratory rate (respiration belt around the chest), GSR (electrodes on the hand), heart rate (pulse-ox), and end-tidal CO2 (nasal cannula).

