Resting State-fMRI: During acquisition of rsfMRI data, participants will be asked to remain awake with their eyes open, viewing a static fixation cross. Though resting state connectivity is highly reproducible over time in healthy participants (Damoiseaux et al., 2006), experience-based neural plasticity in resting state connectivity has been shown to occur over periods as short as 2-9 days. To measure cardiac and respiratory signals, a pulse oximeter and respiratory bellows will be fitted to participants prior to the fMRI sessions. Non-neuronal physiological artefacts (including cardiac and respiratory effects) will be eliminated.

Preprocessing and Analysis: Preprocessing of all fMRI data will follow similar workflows using adapted HCP minimal processing pipelines (www.humanconnectome.org). Specifically, preprocessing steps incorporating FSL (Jenkinson, Beckmann, Behrens, Woolrich, & Smith, 2012; S. M. Smith et al., 2004; Woolrich et al., 2009) and custom processing modules will include: a) removal of non-brain tissue; b) rigid-body head motion correction; c) spatial smoothing (5-6 mm FWHM); d) demising and high pass filtering using FSL's MELODIC; and d) corregistration of the BOLD and T1 images using the matched bandwidth EPI images for intermediate registration. First-level analysis will include the modeling of activation between task conditions (e.g. 0-back vs. 2-back). Temporal derivatives and the 6 motion parameters will be included as covariates of no interest to improve statistical sensitivity. Second-level (fixed effects) and third-level (mixed effects) analyses will average runs within participants and between groups, respectively. *Longitudinal analysis:* In addition to subtracting changes in

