activation between baseline and follow-up scans within individuals for subsequent group comparisons, we will represent fMRI maps as statistical change maps in time. These maps will be presented against the structural template, to determine the effects of structural change, functional change, and their interaction. One sample ttests will determine whether activation for each individual changes significantly over time. Task-related connectivity analysis: To investigate effective "functional" connectivity, we will determine differences in taskdependent functional connectivity between regions-of-interest (ROIs). Using seeds for the hippocampus, ACC and DLPFC, we will investigate within-ROI activity and seed-based connectivity across the brain for working memory load compared to no load (2-back vs. 0-back). Similarly, we will contrast ROI activity and functional connectivity of learned with novel face-name associations. Additionally, encoding-related activity/connectivity will be investigated while subjects study face-name pairs. Group-level FSL FEAT analyses will produce statistical maps indicating voxels throughout the brain showing significantly correlated task-dependent activity with the ROI. Regressors include the ROI (e.g., hippocampus activity), the cognitive variable (0-back vs. 2-back condition and learned vs. novel face-name associations), and their interaction. Higher-level analyses will determine the degree of functional coupling among treatment groups. Resting state analysis: After applying preprocessing steps similar to the described above, widely documented independent components analysis (ICA) (De Luca, Beckmann, De Stefano, Matthews, & Smith, 2006; Greicius et al., 2007) using FSL's MELODIC, will estimate the optimal number of components for each subject and to

remove components representing artifacts. After low pass filtering (0.1-0.01 Hz) and transformation into atlas space, the bestfit DMN, executive and salience, and fronto-

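### The fMRI plan tests change for each individual woman, but one session per time point leaves only within-scan error for that test, so individual statements of significant change would exceed their nominal error rate (minor; wording fix)

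*Combined protocol and SAP*

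**What the plan says.** The Longitudinal analysis text under Preprocessing and Analysis describes two uses of the repeat scans. The first is subtraction of "activation between baseline and follow-up scans within individuals for subsequent group comparisons". In addition, maps of change over time are to be produced for individuals, and "One sample ttests will determine whether activation for each individual changes significantly over time".

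The same section sets out the model levels: "Second-level (fixed effects) and third-level (mixed effects) analyses will average runs within participants and between groups, respectively". Random variation therefore enters only at the group level.

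On data collection, Imaging Biomarkers says "Imaging data will be acquired from each subject" "at baseline and at 12- weeks postrandomization", and "Each scanning session will last 60 minutes". Table 4 marks fMRI at baseline and week 12 only. The imaging sequence table has one N-back acquisition ("task fMRI N-back", 10 minutes) and one face-naming acquisition (5:25). Only resting state has two runs, and both fall in the same session.

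For the individual tests the documents give no unit of observation, repeat-scan variance, reliable-change threshold or significance level.

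**The concern.** A one-sample t-test needs replicate values of the thing being tested. For one woman that is her week-12-minus-baseline change, and the design gives her one such value per contrast and voxel or region. The test can be run for her only by taking replicates from inside the scans, such as volumes or task blocks.

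An error term built that way measures noise within a scan. It does not measure how much the same woman's response would differ between two sessions for ordinary reasons such as alertness, head position or familiarity with the task. That variation adds to the observed difference but not to the standard error.

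What is at stake is any statement that a named number of women, or a particular woman, showed significant change in activation. In a trial with mechanistic aims such a statement could be taken as a sign of an intervention effect when it reflects scan-to-scan variation.

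**Working it through.** The documents give no error rate, variance or number of observations for these tests, so there is no figure of the plan's own to reproduce. The check is of what error rate the test, as worded, would have.

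**Inputs**
- Imaging time points: 2 (Imaging Biomarkers; Table 4).
- Sessions per time point: 1 (Imaging Biomarkers).
- Task runs per session: 1 N-back and 1 face naming (imaging sequence table).
- Nominal level: two-sided 0.05. The Data analysis section ties this to the primary analyses. Using it for the individual fMRI tests is an assumption.
- k: session-to-session variance of the estimated change divided by its within-scan variance. It is not in the documents and is assumed over a range.

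**Step 1: degrees of freedom.** One change value per woman gives n − 1 = 1 − 1 = 0 degrees of freedom. The test cannot be run on her change value itself, so its error must come from within the scans.

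**Step 2: error rate with within-scan error only.** Suppose the woman has no change beyond ordinary session-to-session variation. Her estimated change has variance σ_w² + σ_s² = σ_w²(1 + k), where σ_w² is the within-scan part and σ_s² the session part. The test divides by σ_w alone, so its statistic has variance 1 + k instead of 1. The true two-sided error is

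2 × [1 − Φ(1.96 / √(1 + k))]

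| k | √(1 + k) | 1.96 / √(1 + k) | True error |
|---|---|---|---|
| 0 | 1.000 | 1.960 | 5.0% |
| 0.25 | 1.118 | 1.753 | 8.0% |
| 0.5 | 1.225 | 1.600 | 10.9% |
| 1 | 1.414 | 1.386 | 16.6% |
| 2 | 1.732 | 1.132 | 25.8% |

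Only k = 0 keeps the nominal level.

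**Step 3: simulation check.** With 20 within-scan contrasts per session and 20,000 replicates, the individual t-test rejected 5.2%, 10.7%, 15.4% and 24.3% of the time at k = 0, 0.5, 1 and 2. These are close to the formula. The values for k above 0 are slightly lower, as expected with a t rather than a normal reference.

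**Step 4: can more within-session data cure it?** No. Runs or blocks in one session share that session's offset. A 10-minute run at the stated 720 ms repetition time has 600 / 0.72 ≈ 833 volumes. A longer run shrinks σ_w² but leaves σ_s² alone, so k rises with scan length.

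**Step 5: the same test with the woman as the unit.** A one-sample t-test across 45 simulated change values rejected 4.8% to 5.4% of the time for k from 0 to 4. Session variance is then part of the spread between women, so the standard error includes it. The 45 is the expected completers per group in the Power analysis and serves only as a simulation size.

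**The case against.** The strongest reply is that the literal test cannot be run on one difference, so the authors probably meant a one-sample test of the subtraction maps across women. That would be valid, and it fits the group use of those maps described in the same passage. This may well be the intent. But the sentence names the individual as the unit and follows a separate statement about group comparisons, so an analyst working from the text could run the unsound version.

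A second reply is that a contrast of two sessions within one woman is a legitimate description of how those sessions differed. That stands. The plan speaks of change over time and does not say lasting change. The excess error arises when a significant result is read as change beyond ordinary session variation.

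A reader might infer that Hypothesis 3a goes untested or is undermined. The documents do not support this. The hypothesis, "Compared to MET, KK+KY will be associated with greater improvement in connectivity in regions associated with working and episodic memory", concerns connectivity between arms, and mixed-effects and other group-level analyses are planned for it. Nothing says the individual tests address it.

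A reader might also infer that the mechanistic conclusions rest on these p-values, or that a count of women who changed will be reported. Neither is stated. The planned links to cognition use general linear models for each imaging method and regressions on changes in the measures.

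Finally, a reader might suppose that voxels in a region would serve as independent replicates, with far larger error. No section proposes that.

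**Conclusion.** The point holds in a limited form, and it is minor. As worded, the individual test is anti-conservative for any k above 0: about 8% at k = 0.25, 11% at 0.5, 17% at 1 and 26% at 2, against a nominal 5%.

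The direction follows from the design. The size does not, because it rests on an assumed k and an assumed 5% level for these tests. The figures are therefore a range over inputs and not an estimate for this trial. Nor can they be turned into an expected number of women flagged, since Compensation pays separately for those who complete fMRI scans and the documents do not settle how many will.

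The consequence is confined to individual-level statements of significant change in activation. The planned group comparisons, the primary outcome and the other stated outcomes do not depend on these tests.

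**What to change.** Replace the sentence on one-sample t-tests with:

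> One-sample t-tests across women, with the woman as the unit, will estimate mean week-12-minus-baseline change in activation within each arm (descriptive). Inference on intervention effects rests on the planned between-arm mixed-effects comparison of the change maps. Individual change maps are descriptive, without significance statements.

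This needs no new data, because the within-woman subtractions and group comparisons are already planned. If the intent was always a test across women, the edit only makes that explicit. The cost is that no individual-level p-value can be reported. Keeping one would require an estimate of session-to-session variance from repeat scans, which the design does not include.
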